5.2 SERIOUS ADVERSE EVENTS

The term “Serious Adverse Event” (SAE) is defined in 21 CFR 312.32 as follows: “An adverse event or suspected adverse reaction is considered serious if, in the view of either the investigator or the sponsor, it results in any of the following outcomes: Death, a life-threatening adverse event, inpatient hospitalization or prolongation of existing hospitalization, a persistent or significant incapacity or substantial disruption of the ability to conduct normal life functions, or a congenital anomaly/birth defect. Important medical events that may not result in death, be life-threatening, or require hospitalization may be considered serious when, based upon appropriate medical judgment, they may jeopardize the patient or subject and may require medical or surgical intervention to prevent one of the outcomes listed in this definition. Examples of such medical events include allergic bronchospasm requiring intensive treatment in an emergency room or at home, blood dyscrasias or convulsions that do not result in inpatient hospitalization, or the development of drug dependency or drug abuse.”

“Life-threatening” refers to an AE that at occurrence represents an immediate risk of death to a

subject. An event that may cause death if it occurs in a more severe form is not considered life-threatening. Similarly, a hospital admission for an elective procedure is not considered a SAE.

5.3 ADVERSE EVENT REPORTING TO THE IND SPONSOR

AEs that meet Serious Adverse Event (SAE) Reporting Requirements must be reported and submitted by the clinical site on an expedited basis to the IND Sponsor, VRC/NIAID/NIH, according to Sponsor guidelines as follows:

- results in death
- is life threatening
- results in persistent or significant disability/incapacity
- requires unplanned inpatient hospitalization or prolongation of existing hospitalization
- is a congenital anomaly/birth defect in the offspring of a study subject
- is an important medical event that may jeopardize the subject or may require intervention to prevent one of the other outcomes listed above.

In addition, any event, regardless of severity, which in the judgment of an investigator represents a SAE, may be reported on an expedited basis.

An investigator will communicate an initial SAE report within 24 hours of site awareness of occurrence to the IND sponsor by email to the VRC Protocol Operations Office (see [Appendix II](#)).

A written report by the investigator should be submitted to the IND Sponsor within 3 working days. In order for the IND Sponsor to comply with regulations mandating sponsor notification of specified SAEs to the FDA within 7 and/or 15 calendar days, the investigator must submit additional information as soon as it is available.

5.3.1 IND Sponsor Reporting to the FDA

It is the responsibility of the IND Sponsor to make the determination of which SAEs are “serious and unexpected suspected adverse reactions” (SUSARs) as defined in 21 CFR 312.32.

- *Suspected adverse reaction* means any AE for which there is a reasonable possibility that the drug caused the AE.
- *Unexpected Adverse Event* means an AE that is not listed in the IB or is not listed at the specificity or severity that has been observed.

All SUSARs, as determined by the IND Sponsor, will be reported to the FDA as IND Safety Reports and IND Safety Reports will be provided to the IRB.

The IND Sponsor will also submit an IND Annual Report of the progress of the investigation to the FDA as defined in 21 CFR 312.33.

5.4 REPORTING TO THE INSTITUTIONAL REVIEW BOARD

5.4.1 Unanticipated Problem (UP) Definition

A serious “Unanticipated Problem (UP)” is defined as any incident, experience, or outcome that meets all three of the following criteria:

- unexpected in nature, severity, or frequency in relation to the research risks that are described in the protocol, informed consent, IB, other study documents or in consideration of the characteristics of the subject population being studied; **and**
- related to participation in the research; **and**
- suggests that the research places subjects or others at a greater risk of harm (including physical, psychological, economic, or social harm) than was previously known or recognized.

Non-serious UP: An UP that is not an Adverse Event (UPnonAE) is an unanticipated problem that does not fit the definition of an AE, but which may, in the opinion of the investigator, involve risk to the subject, affect others in the research study, or significantly impact the integrity of research data. Such events would be considered a non-serious UP. For example, we will report occurrences of breaches of confidentiality, accidental destruction of study records or samples, or unaccounted-for study drug.

5.4.2 Protocol Deviation Definition

A Protocol Deviation is defined as any change, divergence, or departure from the IRB-approved study procedures in a research protocol. Protocol deviations are designated as serious or non-serious and further characterized as follows:

- Those that occur because a member of the research team deviates from the protocol.
- Those that are identified before they occur, but cannot be prevented.
- Those that are discovered after they occur.

Serious Protocol Deviation: A deviation that meets the definition of a SAE or compromises the safety, integrity of the data, welfare or rights of subjects or others.

5.4.3 Non-Compliance Definition

Non-compliance is the failure to comply with applicable NIH Human Research Protections Program (HRPP) policies, IRB requirements, or regulatory requirements for the protection of human subjects. Non-compliance is further characterized as serious, continuing or minor.

“Serious non-compliance” is defined as non-compliance that:

- Increases risks, or causes harm, to participants
- Decreases potential benefits to participants
- Compromises the integrity of the NIH-HRPP
- Invalidates the study data

“Continuing non-compliance” is non-compliance that is recurring.

“Minor non-compliance” is non-compliance that is neither serious nor continuing.

5.4.4 Expedited Reporting to the NIAID IRB

The following will be reported within 7 calendar days of investigator awareness:

- Serious and non-serious UP

- Deaths
- Serious protocol deviations
- Serious or continuing non-compliance
- SAEs that are possibly, probably, or definitely related to the research regardless of expectedness

The following waiver applies to reporting anticipated protocol deviations and expected UPnonAEs: Anticipated deviations in the conduct of the protocol will not be reported to the IRB unless they occur at a rate greater than anticipated by the study team. Expected AEs will not be reported to the IRB unless they occur at a rate greater than that known to occur in healthy adults. If the rate of these events exceeds the rate expected by the study team, the events will be classified and reported as though they are unanticipated problems.

5.4.5 Annual Reporting to the NIAID IRB

The following will be reported to the NIAID IRB in summary at the time of Continuing Review:

- Serious and non-serious UPs
- Expected SAEs that are possibly, probably, or definitely related to the research
- SAEs that are not related to the research
- All AEs, except expected AEs granted a waiver of reporting
- Serious and non-serious Protocol Deviations
- Serious, continuing, and minor non-compliance
- Any trends or events which in the opinion of the investigator should be reported

6. STATISTICAL CONSIDERATIONS

6.1 OVERVIEW

This is a Phase I dose-escalation study of the safety and pharmacokinetics of VRC-HIVMAB075-00-AB (VRC07-523LS), a human monoclonal antibody with broad HIV-1 neutralizing activity, administered to healthy adults.

6.2 OBJECTIVES

The primary objective is to evaluate the safety and tolerability of VRC07-523LS administered at 1 mg/kg IV, 5 mg/kg IV, 5 mg/kg SC, 20 mg/kg IV and 40 mg/kg IV as a single dose, and administered at 20 mg/kg IV and 5 mg/kg SC by repeat dosing every 12 weeks for a total of 3 product administrations to healthy adults. Secondary objectives include evaluation of the PKs at each dose level through 24 weeks after the last dose and testing for the presence of ADA against VRC07-523LS. Exploratory objectives include determining if measurable levels of VRC07-523LS can be found in oral secretions, evaluation for evidence of functional activity of VRC07-523LS in collected samples, and evaluation of allotype-specific effects on the VRC07-523LS pharmacokinetics.

6.3 SIZE AND ACCRUAL

Recruitment will target about 25 healthy adults of age 18-50 with 3 subjects in each dose escalation group (Groups 1-5), and 5 subjects in each repeat dosing group (Groups 6 and 7). The permitted accrual is 40 subjects to allow for additional enrollments in the event that an enrolled subject does not complete the minimum evaluations needed to meet the protocol criteria for the group dose safety or dose escalation evaluation.

6.3.1 Treatment Assignments

In this dose-escalation study, subjects will be assigned to the dose group that is open to accrual at the time of enrollment.

When a subject is enrolled into a group but does not begin product administrations, a new eligible subject may be enrolled into the same group. If any replacement is needed in case of subject withdrawal, the replacement subject will be assigned to the same treatment as the dropout subject in order to complete the safety dataset as planned.

Dose escalation rules are described in Section 4.3.

6.3.2 Sample Size Considerations

This study is primarily descriptive. For safety analysis, the goal is to identify safety concerns associated with different VRC07-523LS doses. There may be as few as 3 to 5 subjects in a group at the time of a dose escalation; therefore, this section considers group sizes of both n=3 and n=5.

The ability to identify serious adverse experiences is best expressed by the maximum true rate of SAE that would unlikely be observed and the minimum true SAE rate that would very likely be observed. Within a group of size n=3, there is a 90% chance of observing at least 1 event if the true rate is no less than 0.536 and a 90% chance of observing no event if the true rate is no bigger than 0.034. Within a group of size n=5, there is a 90% chance of observing at least 1 event if the true rate is no less than 0.37 and a 90% chance of observing no event if the true rate is no bigger than 0.02.

Probabilities of observing 0 or more than 1 event are presented in Table 4 for a range of possible true event rates. These calculations provide a complete picture of the sensitivity of this study design to identify potential safety problems with the study product. For example, within the group of size n=3, if the true event rate is 0.01, then there is a probability of 0.97 to observe no event and a probability of <0.001 to observe more than 1 event; while, within the group of size n=5, if the true event rate is 0.01, then there is a probability of 0.951 to observe no event and a probability of 0.001 to observe more than 1 event.

Table 4: Probability of Event for Different Scenarios

True event rate	Within a group (n=3)		Within a group (n=5)	
	Pr(0 event observed)	Pr(more than 1 event observed)	Pr(0 event observed)	Pr(more than 1 event observed)
0.01	0.97	0	0.951	0.001
0.03	0.913	0.003	0.859	0.008
0.05	0.857	0.007	0.774	0.023
0.1	0.729	0.028	0.59	0.081
0.2	0.512	0.104	0.328	0.263
0.3	0.343	0.216	0.168	0.472
0.4	0.216	0.352	0.078	0.663

Table 5 gives the upper and lower bounds for 95% exact binomial confidence intervals for all possible number of observed events within a group. Within the group of size n=3, if no subjects experience the event, the 95% exact 2-sided confidence interval for the true rate has upper bound as 0.708; if all subjects experience the event, the 95% exact 2-sided confidence interval for the true rate has lower bound as 0.292. Within the group of size n=5, if no subjects experience the event, the 95% exact 2-sided confidence interval for the true rate has upper bound as 0.522; if all subjects experience the event, the 95% exact 2-sided confidence interval for the true rate has lower bound as 0.478.

Table 5: 95% Confidence Intervals of the True Rate for All Possible Number of Observed Events within a Group

Within a group (n=3) 95% confidence interval			Within a group (n=5) 95% confidence interval		
Observed rate	Lower bound	Upper bound	Observed rate	Lower bound	Upper Bound
0/3	0	0.708	0/5	0	0.522
1/3	0.008	0.906	1/5	0.005	0.716
2/3	0.094	0.992	2/5	0.053	0.853
3/3	0.292	1	3/5	0.147	0.947
			4/5	0.284	0.995
			5/5	0.478	1

Tables 4 and 5 apply to the secondary and exploratory endpoints as well.

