4.5 CRITERIA FOR PAUSING THE STUDY AND RESUMING THE STUDY

Administration of the study product and new enrollments will be paused by the PI according to the criteria noted below. In the event of a pause, the IND Sponsor Medical Officer (MO) and the PSRT will be promptly notified. Pause criteria are as follows:

One (or more) subject experiences a **Serious Adverse Event** (SAE) that is assessed as related to study product, or

Two (or more) subjects experience the same **Grade 3 or higher AEs** assessed as related to study product (other than self-limited Grade 3 solicited reactogenicity AEs).

Plan for Review of Pauses and Resuming Rules:

Study product administration and enrollments would resume only if review of the AEs that caused the pause results in a recommendation to permit further study product administrations and study enrollments. The reviews to make this decision will occur as follows:

Pauses for related SAEs: The IND Sponsor, with participation by the PI, will consult with the FDA to conduct the review and make the decision to resume, amend or close the study and will notify the IRB accordingly.

Pauses for Grade 3 or higher related AEs: The IND Sponsor MO, in consultation with the PI, will conduct the review and make the decision to resume, amend or close the study for the Grade 3 or higher AEs that meet criteria for pausing the study. As part of the pause review, the reviewers will also advise on whether the study needs to be paused again for any subsequent events of the same type. The FDA and the IRB will be notified of Grade 3 or higher pause reviews and of the IND Sponsor's decisions.

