6.4.3 Safety Analysis

Summaries of the number and percentage of subjects experiencing any AE or reactogenicity will be tallied by subgroup, and presented along with exact 95% confidence intervals for the proportion.

Solicited AEs: Solicited AE data is collected after each dose administered in this study. The number and percentage of subjects experiencing each type of solicited sign or symptom will be tabulated by severity. For a given sign or symptom, each subject's solicited AEs will be counted once under the maximum severity for all assessments.

Unsolicited AEs: Unsolicited AEs are coded into MedDRA preferred terms. The number and percentages of participants experiencing each specific AE will be tabulated by severity and relationship to treatment. For the calculations in these tables, each participant's adverse experience will be counted once under the maximum severity or strongest recorded causal relationship to treatment.

A complete listing of adverse experiences for each participant will provide details including severity, relationship to treatment type, onset, duration and outcome.

Local Laboratory Values: Boxplots of local laboratory values will be generated for baseline values and for values measured during the course of the study. Each boxplot will show the 1st quartile, the median, and the 3rd quartile. Outliers, or values outside the boxplot, will also be plotted. If appropriate, horizontal lines representing boundaries for abnormal values will be plotted.

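### Section 6.3.2 presents within-group probabilities as the design's full safety sensitivity, and Section 6.4.3 names no pooled first-dose safety rows although two pairs of groups share dose and route

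*Combined protocol and SAP*

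**What the plan says.** Section 6.3.2 gives its reason for working with small groups: "There may be as few as 3 to 5 subjects in a group at the time of a dose escalation". All its calculations accordingly use a group of 3 or a group of 5. On the content of Table 4 it says: "Probabilities of observing 0 or more than 1 event are presented in Table 4 for a range of possible true event rates". Both halves of that table, and Table 5, are labelled as within a group. The text adds detection limits. For n=3, "there is a 90% chance of observing at least 1 event if the true rate is no less than 0.536"; for n=5, "there is a 90% chance of observing at least 1 event if the true rate is no less than 0.37". It then sums up: "These calculations provide a complete picture of the sensitivity of this study design to identify potential safety problems with the study product".

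Section 4.5 pauses all product administration and new enrollment on either of two triggers. The first is one or more subjects with a related SAE. The second begins "Two (or more) subjects experience the same" and refers to related AEs of Grade 3 or higher, leaving out self-limited Grade 3 solicited reactogenicity. Neither trigger is tied to a group or dose.

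Section 6.4.3 says: "Summaries of the number and percentage of subjects experiencing any AE or reactogenicity will be tallied by subgroup", with exact 95% confidence intervals. It does not define subgroup and names no pooled or overall row.

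Section 4 (Table 3) gives Groups 4 (n=3) and 7 (n=5) 20 mg/kg IV on Day 0, and Groups 3 (n=3) and 6 (n=5) 5 mg/kg SC on Day 0. Expected enrollment is 25, with up to 40 permitted.

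**The concern.** The summing-up sentence in Section 6.3.2 is about the study design, but the calculations behind it are about one group at a time. A reader who wants to know how likely the trial is to pause, or what the trial as a whole can say about a rare event, will not find it there or elsewhere in the documents.

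The reporting plan has the same limit. The first primary objective (Section 3.1) is single-dose safety at each dose and route. For two of those five dose-route combinations the study will dose 8 people identically on Day 0, yet Section 6.4.3 commits only to intervals by subgroup. If subgroup means study group, those 8 are split into 3 and 5, and the planned intervals for the primary safety result are much wider than the collected data allow.

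**Working it through.** **1. The plan's own figures.** With n subjects and true rate p, Pr(0) = (1−p)^n and Pr(more than 1) = 1 − (1−p)^n − np(1−p)^(n−1). At p = 0.1:

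- n=3: Pr(0) = 0.9^3 = 0.729; Pr(more than 1) = 3(0.01)(0.9) + 0.001 = 0.028.
- n=5: Pr(0) = 0.9^5 = 0.590; Pr(more than 1) = 1 − 0.5905 − 0.3281 = 0.081.

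All 28 entries of Table 4 reproduce, as does Table 5 by the Clopper-Pearson method. The 90% detection limits are 1 − 0.1^(1/3) = 0.536 and 1 − 0.1^(1/5) = 0.369 (printed as 0.37). Nothing in either table is wrong.

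**2. Upper 95% limit after zero events.** The exact two-sided limit is 1 − 0.025^(1/n).

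| Rows | n | Upper limit |
|---|---|---|
| Group of 3 (Table 5) | 3 | 0.708 |
| Group of 5 (Table 5) | 5 | 0.522 |
| Groups 4+7, or Groups 3+6, first dose | 3+5 = 8 | 0.369 |
| All subjects | 25 | 0.137 |

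**3. Can the pairs be pooled for the first dose?** Dose and route on Day 0 are identical within each pair. Section 5.1 collects all AEs for 56 days after each administration. The second dose in Groups 6 and 7 is due at Day 84 with a 7-day window, so at the earliest on Day 77. The 56-day window therefore closes before any second dose, and all 8 subjects have the same nominal all-AE reporting period. One small difference remains: Groups 3 and 4 have a Week 3 visit (Visit 08) that Schedules 3 and 4 omit.

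**4. What Table 4 leaves out about the pause rules.** Assume independent subjects and one common per-subject rate across doses and routes.

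- Rule 1 (at least one related SAE): 1 − (1−p)^N. At p = 0.01 this is 1 − 0.99^25 = 0.222 for N=25 and 1 − 0.99^40 = 0.331 for N=40. The complements of Table 4's Pr(0) at that rate are 0.030 (n=3) and 0.049 (n=5). One SAE in any group triggers the rule, so counting by group or study-wide gives the same answer.
- Rule 2 (at least two subjects with the same event): at p = 0.1, 1 − 0.9^25 − 25(0.1)(0.9^24) = 1 − 0.0718 − 0.1994 = 0.729 for N=25, and 0.920 for N=40. Table 4 has 0.028 and 0.081. Here p must be the rate of one specific related Grade 3 or higher AE. If the rule were instead applied group by group, the chance that any of the seven groups met it would be 1 − (1−0.028)^5 × (1−0.0815)^2 = 0.268.

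**The case against.** The strongest reply is that Section 6.3.2 does what it sets out to do. It ties its group sizes to the numbers available at an escalation, and Section 4.3 sets each dose escalation review at a minimum of 3 subjects on the current dose. At the first review, 3 subjects may be all the data there are. The study is descriptive, no pause threshold is derived from Table 4, and the omission understates sensitivity, so it gives no false reassurance. Pooling all 25 also assumes away the dose effect that the study is meant to look for. All of this stands.

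Several stronger readings fail for these reasons:

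- A reader might infer that the true pause probabilities contradict those in the plan. The documents state none, and Table 4 does not claim to give them.
- A reader might infer that Table 4 is wrong for the decisions taken. It is correct, it is labelled by group, and n=3 is the minimum for a dose escalation review.
- A reader might infer that an overall safety figure will never be reported. Section 6.4.3 does not forbid one. Its solicited and unsolicited AE paragraphs carry no group restriction, and it promises a full AE listing. A pooled row with an interval is simply not named.

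The reply does not reach the two same-dose, same-route pairs. Pooling their first-dose data mixes neither dose nor route, and the plan already thinks this way elsewhere: the third escalation review in Section 4.3 counts subjects who received 20 mg/kg IV, not members of Group 4, and Section 6.4.5 summarizes some PK parameters across all IV groups.

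**Conclusion.** The point holds as one overbroad sentence and one missed, inexpensive summary. It is not an error in any figure. The useful part is the pooled first-dose rows: for 20 mg/kg IV and for 5 mg/kg SC, the upper limit after zero events falls from 0.708 or 0.522 to 0.369, using data already being collected. That rests on 8 dosed subjects per pair and on limiting the rows to the shared 56-day window. An overall row reaches 0.137 at n=25, but it describes a mixture of doses and routes and cannot replace the group rows.

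The pause-rule figures are conditional on a common rate, on independence and, for the second rule, on one specific AE type. That the second rule counts across the whole study is read from the absence of any group limit in Section 4.5. These figures show that the pause behaviour cannot be read from Table 4. They do not show that the rules are badly set.

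**What to change.** 1. In Section 6.4.3, keep the by-group rows and add pooled first-dose rows for Groups 4+7 (20 mg/kg IV) and Groups 3+6 (5 mg/kg SC). Restrict them to AEs within 56 days after the first dose, label them as pooled, and give exact 95% intervals on the number actually dosed.
2. Add an overall row with an exact 95% interval, labelled as mixing doses and routes and secondary to the by-group rows. Define subgroup.
3. In Section 6.3.2, limit the summing-up sentence to within-group sensitivity.
4. Optionally, add study-wide probabilities for the two pause rules at N=25 and N=40, with the assumptions of independent subjects, one common rate across doses and routes and, for the second rule, the rate of one specific related Grade 3 or higher AE.

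The cost is a few table rows and one reworded sentence. No extra data, subjects or design changes are needed. The downside is that the overall row could be over-read, which the labelling is meant to prevent.
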